2.4.5.2 Deaths

The following summaries of deaths will be generated for the safety population.

- Number (%) of patients who died by study period (on-study, on-treatment, poststudy)
- Deaths in nonrandomized patients or randomized but not treated patients
- Treatment-emergent adverse events leading to death (death as an outcome on the adverse event case report form page as reported by the Investigator) by primary SOC , HLG, HLT, and PT showing number (%) of patients sorted by internationally agreed SOC order, with HLG, HLT, and PT presented in alphabetical order within each SOC .
- All pretreatment adverse events leading to death by primary SOC and PT, showing the number (%) of patients, sorted by the internationally agreed SOC order and decreasing incidence of PTs within each SOC

A listing of deaths will be provided.

2.4.5.3 Analyses of laboratory variables

The summary statistics (including number, mean, median, Q1, Q3, standard deviation, minimum and maximum) of all laboratory variables (central laboratory values and changes from baseline) will be calculated for each visit or study assessment (baseline, each postbaseline time point, last on-treatment and/or worst on-treatment value) by treatment group. For each continuous parameters listed in [Section 2.1.4.3](#), mean changes from baseline with the corresponding standard error will be plotted over time in each treatment group. This section will be organized by biological function as specified in [Section 2.1.4.3](#).

The incidence of PCSAs (list provided in [Appendix A](#)) at any time during the treatment-emergent adverse event period will be summarized by biological function and treatment group whatever the baseline level and/or according to the following baseline status categories:

- Normal/missing
- Abnormal according to PCSA criterion or criteria

The incidence of PCSAs from baseline to Week 24 during the treatment-emergent adverse event period will be summarized by biological function and treatment group whatever the baseline level and/or according to the following baseline status categories:

- Normal/missing
- Abnormal according to PCSA criterion or criteria

For parameters for which no PCSA criteria are defined, similar table(s) using the normal range will be provided.

For PCSA analyses, the laboratory measurements obtained at either scheduled or unscheduled visits should be used; and, both the centralized and local test results should be used, as long as their available dates/time is different from each other's. Centralized data will be used preferentially to the local measures in the PCSA analyses when measurements are performed on the same date and at the same time for a given laboratory test.

Possible Drug-induced liver injury

If there is any imbalance in the incidence of liver-related adverse events across the treatment groups, analysis of liver-related adverse events will be performed.

The liver function tests, namely AST, ALT, alkaline phosphatase, and total bilirubin, are used to assess possible drug-induced liver toxicity. The proportion of patients with PCSA values at any postbaseline visit by baseline status will be displayed by treatment group for each parameter. The proportion of patients with PCSA values at any postbaseline visit will also be displayed by duration of exposure for each treatment group.

Time to onset of the initial ALT and AST elevation (>3 x ULN) and total bilirubin elevation (>2 x ULN) (time to first observation of ALT >3 x ULN or total bilirubin >2 x ULN, whichever comes first) will be analyzed using Kaplan-Meier estimates, presented by treatment group. Consideration should be given to the impact of the spacing of scheduled tests. A graph of distribution of peak values of ALT versus peak values of total bilirubin will also be presented. Note that the ALT and total bilirubin values are presented on a logarithmic scale. The graph will be divided into 4 quadrants with a vertical line corresponding to 3 x ULN for ALT and a horizontal line corresponding to 2 x ULN for total bilirubin.

Listing of possible Hy's law cases identified by treatment group (eg, patients with any elevated ALT >3 x ULN, and associated with an increase in bilirubin ≥ 2 x ULN) with ALT, AST, alkaline phosphatase, total bilirubin, and the following complementary parameters: conjugated bilirubin and creatine phosphokinase, serum creatinine, complete blood count, HCV RNA.

Summarize the normalization by parameter (to ≤ 1 x ULN or return to baseline) of elevated liver function tests by categories of elevation (3 x, 5 x, 10 x, 20 x ULN for ALT and AST, 1.5 x ULN for alkaline phosphatase, and 1.5 x and 2 x ULN for total bilirubin), with the following categories of normalization: never normalized, normalized despite treatment continuation of IMP, or

normalized after IMP discontinuation. Note that a patient will be counted only under the maximum elevation category.

2.4.5.4 Analyses of vital sign variables

The summary statistics (including number, mean, median, Q1, Q3, standard deviation, minimum and maximum) of all vital signs variables (values and changes from baseline) will be calculated for each visit or study assessment (baseline, each postbaseline time point, last on-treatment and/or worst on-treatment value) by treatment group. For all parameters, mean changes from baseline with the corresponding standard error will be plotted over time (at same time points) in each treatment group.

The incidence of PCSAs at any time during the treatment-emergent adverse event period will be summarized by treatment group irrespective of the baseline level and/or according to the following baseline status categories:

- Normal/missing
- Abnormal according to PCSA criterion or criteria

The incidence of PCSAs from baseline to Week 24 during the treatment-emergent adverse event period will be summarized by treatment group irrespective of the baseline level and/or according to the following baseline status categories:

- Normal/missing
- Abnormal according to PCSA criterion or criteria

2.4.5.5 Analyses of electrocardiogram variables

The incidence of PCSAs at any time during the treatment-emergent adverse event period will be summarized by treatment group irrespective of the baseline level and/or according to the following baseline status categories:

- Normal/missing
- Abnormal according to PCSA criterion or criteria

The incidence of PCSAs from baseline to Week 24 during the treatment-emergent adverse event period will be summarized by treatment group irrespective of the baseline level and/or according to the following baseline status categories:

- Normal/missing
- Abnormal according to PCSA criterion or criteria

2.4.6 Analyses of pharmacokinetic and pharmacodynamic variables

2.4.6.1 Pharmacokinetic analyses

2.4.6.1.1 Analyses of serum concentrations of SAR231893 (REGN668)

Serum concentrations of SAR231893 (REGN668) will be summarized in the PK population using arithmetic and geometric means, SD, standard error of the mean (SEM), coefficient of variation (CV), minimum, median and maximum per sampling time. If date and/or time of the drug injection and/or sampling is missing then the concentration will not be taken into account. For drug-treated patients, where concentration values are below the lower limit of quantification (LLOQ), one-half of the LLOQ will be used. Values will be expressed in the tables with no more than three significant figures. For patients in the placebo group, concentration values are below the LLOQ will be taken into account with a plasma concentration considered equal to 0.

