In the ACT12340 study, a gradual development of treatment response was observed for bilateral NPS and NP symptoms of NC and sense of smell. The PD steady-state for the above endpoints was not reached at the end of treatment (EOT) at Week 16, suggesting additional therapeutic benefit with longer treatment duration. The time-course PK/PD analysis predicts 24 weeks to be the optimal treatment duration to assess the maximal symptomatic effect for NPS, NC, and other key secondary efficacy endpoints. In addition, a persistent off-treatment effect for dupilumab was also observed, where clinically relevant improvement in the primary and secondary endpoints as compared to the baseline was sustained at the end of the 16-week follow-up when dupilumab concentration already became undetectable. This suggested that a dose regimen given less frequently might sustain a full treatment response. Therefore, the current study will assess both the long term efficacy of the 300 mg q2w treatment for a 52-week period, as well as the maintenance of efficacy at a less frequent 300 mg q4w dosing regimen starting after an initial 24-week "induction" treatment period with 300 mg q2w and continuing until completion of a total treatment duration of 52 weeks.

In the ACT12340, a single loading dose of 600 mg was used on Day 1 to rapidly achieve an efficacious concentration range for a potentially earlier onset of significant response. Consistent with the observed PK and PD profile of NP response (gradual development of response as well as slow offset of response during off-treatment), PK/PD simulation of co-primary endpoints of NPS and NC showed minimal difference in the development of treatment effect and steady-state response of NPS and NC in the presence and absence of a loading dose of 600 mg on Day 1. Therefore, no loading dose is included in the present study.

In summary, the present clinical evidence from the 3 related Th2 disease populations of CRSwNP, AD, and asthma supports selection of 300 mg q2w as the potential efficacious dose regimen to be evaluated for benefit risk in the Phase 3 study.

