#### 7.2.1 Exclusion criteria related to study methodology

- E 01. Patients <18 years of age.
- E 02. Patient who has previously been treated in dupilumab studies.
- E 03. Patient who has taken:
- Biologic therapy/systemic immunosuppressant to treat inflammatory disease or autoimmune disease (eg, rheumatoid arthritis, inflammatory bowel disease, primary biliary cirrhosis, systemic lupus erythematosus, multiple sclerosis, etc.) within 2 months before V1 or 5 half-lives, whichever is longer.
  - Any experimental mAB within 5 half-lives or within 6 months before V1 if the half-life is unknown.
  - Anti-immunoglobulin E therapy (omalizumab) within 130 days prior to V1.
  - Patients who are receiving leukotriene antagonists/modifiers at V1 unless they are on a continuous treatment for at least 30 days prior to V1.

- E 04. Initiation of allergen immunotherapy within 3 months prior to V1 or a plan to begin therapy or change its dose during the run-in period or the randomized treatment period.
- E 05. Patients who have undergone any and/or sinus intranasal surgery (including polypectomy) within 6 months before V1.
- E 06. Patients who have had a sino-nasal surgery changing the lateral wall structure of the nose making impossible the evaluation of NPS.
- E 07. Patients with conditions/concomitant diseases making them non evaluable at V1 or for the primary efficacy endpoint such as:
- Antrochoanal polyps.
  - Nasal septal deviation that would occlude at least one nostril.
  - Acute sinusitis, nasal infection or upper respiratory infection.
  - Ongoing rhinitis medicamentosa.
  - Allergic granulomatous angiitis (Churg-Strauss syndrome), granulomatosis with polyangiitis (Wegener's granulomatosis), Young's syndrome, Kartagener's syndrome or other dyskinetic ciliary syndromes, concomitant cystic fibrosis.
  - Radiologic suspicion, or confirmed invasive or expansive fungal rhinosinusitis
- E 08. Patients with nasal cavity malignant tumor and benign tumors (eg, papilloma, blood boil etc).
- E 09. Patients with forced expiratory volume (FEV1) 50% or less of predicted normal.
- E 10. Patients receiving concomitant treatment prohibited in the study (see [Section 8.8.1](#)).
- E 11. Patient is the Investigator or any Sub-Investigator, research assistant, pharmacist, study coordinator, other staff or relative thereof directly involved in the conduct of the protocol.

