2.1.5 Pharmacokinetic variables

Predose serum dupilumab concentrations at Visit 2 (Day 1), dupilumab trough levels at Week 2, Week 4, Week 16, Week 24, Week 40, Week 52/EOT Visit and posttreatment serum dupilumab at Week 64/EOS Visit will be provided.

Anti-dupilumab antibody (ADA) status (negative or titer value, if positive in the ADA assay) at Visit 2 (Day 1), Week 8, Week 16, Week 24, Week 52 and follow up at Week 64 will be provided. Patients who discontinue early from treatment may be asked to return to the clinic to have additional ADA samples collected for analysis based on the overall clinical presentation at that time.

ADA incidence will be classified as the following:

Pre-existing immunoreactivity are defined as:

An ADA positive response in the assay at baseline with all post treatment ADA results negative, OR an ADA positive response at baseline with all post treatment ADA responses less than 4-fold over baseline titer levels.

Treatment-emergent anti-drug antibodies are defined as:

A positive response in the ADA assay post first dose, when baseline results are negative or missing.

Treatment-emergent ADA responses are further classified as Persistent, Indeterminate or Transient

- a) Persistent Response- defined as a treatment-emergent ADA response with two or more consecutive ADA positive sampling time points, separated by greater than (>) 12-week period (84 days) ,with no ADA negative samples in between.
- b) Indeterminate Response- defined as a treatment-emergent response with only the last collected sample positive in the ADA assay
- c) Transient Response - defined as a treatment-emergent response that is not considered persistent OR indeterminate

Treatment-boosted response is defined as:

An ADA positive response in the assay post first dose that is greater-than or equal to 4-fold over baseline titer levels, when baseline results are positive.

Titer values (Titer value category)

- Low (Titer <1000)
- Moderate ($1,000 \leq \text{Titer} \leq 10,000$)
- High (Titer >10,000)

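### The below-LLOQ rule gives dupilumab patients a concentration of LLOQ/2 before their first dose and placebo patients 0; exempt the predose sample and report how many values are substituted

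*SAP*

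**What the plan says.** SAP 2.4.6.1.1 summarises serum dupilumab per sampling time with arithmetic and geometric means, SD, SEM, CV, minimum, median and maximum. Values below the limit are handled by treatment group: "For drug-treated patients, where concentration values are below the lower limit of quantification (LLOQ), one-half of the LLOQ will be used"; for placebo patients, "concentration values are below the LLOQ will be taken into account with a plasma concentration considered equal to 0". No sampling time is exempt, and no count of values below the limit is planned.

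SAP 2.1.5 includes the predose sample ("Predose serum dupilumab concentrations at Visit 2 (Day 1") and the last one: "posttreatment serum dupilumab at Week 64/EOS Visit will be provided". SAP Table 5 gives the predose sample its own window, up to the first dose. The PK population (SAP 2.3.3) is not restricted to dupilumab patients.

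Protocol 7.2.1 (E 02) excludes this group: "Patient who has previously been treated in dupilumab studies". On washout, Protocol 4.4.2 reports for the earlier phase 2 trial, which used 300 mg weekly, that benefit persisted "at the end of the 16-week follow-up when dupilumab concentration already became undetectable". Neither document makes such a statement about Week 64 of this trial, and neither gives the LLOQ.

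**The concern.** Before the first dose, a result below the limit means the same thing in every arm: no drug. The rule records it as LLOQ/2 in Arms A and B and as 0 in Arm C, so the baseline row shows an arm difference that the substitution alone has created. The rule also feeds zeros into a geometric mean that is planned without distinction by group.

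Further on, with no count of values below the limit, a reader cannot say how many of the values behind a summary were measured. That matters most at Week 64. It can also arise earlier, because Protocol 10.3.1 keeps patients who stop treatment on the scheduled PK sampling. Systemic exposure is a stated secondary objective (Protocol 5.2, SAP 1.2.2), so these tables will be read.

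**Working it through.** The plan states no figure here, so there is nothing to reproduce. All results are in units of LLOQ.

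**Day 1 predose.** Assume every value is below the limit, which the exclusion of earlier dupilumab-study patients makes reasonable.
- Arms A and B: every value is 0.5, so arithmetic mean = geometric mean = median = 0.5, SD = 0 and CV = 0/0.5 = 0%.
- Placebo: every value is 0, so the mean is 0. The geometric mean is 0 as a product and undefined through logarithms.
- With predose values set to 0 in all arms, every mean is 0 and the geometric mean is not estimable in any arm.

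**Time off drug at Week 64.**
- The last injection is at Week 50 (Protocol 8.1.4). Arm A: 64 − 50 = 14 weeks.
- Arm B kits from Week 24 hold an active syringe followed by placebo (Protocol 8.5), so active doses fall at Weeks 24, 28, 32, 36, 40, 44 and 48. Arm B: 64 − 48 = 16 weeks.

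**Week 64 summaries.** Let f be the share below the limit and m a common level for the quantifiable values. Both are assumptions.
- Arithmetic mean = 0.5f + (1 − f)m
- Share of that mean supplied by the rule = 0.5f / [0.5f + (1 − f)m]
- Geometric mean = 0.5^f × m^(1 − f)

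| f | m | Arithmetic mean | Share from rule | Geometric mean |
|---|---|---|---|---|
| 50% | 2 | 1.25 | 20.0% | 1.000 |
| 50% | 10 | 5.25 | 4.8% | 2.236 |
| 50% | 50 | 25.25 | 1.0% | 5.000 |
| 90% | 2 | 0.65 | 69.2% | 0.574 |
| 90% | 10 | 1.45 | 31.0% | 0.675 |
| 90% | 50 | 5.45 | 8.3% | 0.792 |
| 100% | – | 0.50 | 100% | 0.500 |

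The rule supplies half of the arithmetic mean when 0.5f = (1 − f)m, that is f = m/(m + 0.5): 2/2.5 = 80%, 10/10.5 = 95.2% and 50/50.5 = 99.0%.

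The geometric mean gives way sooner. Between m = 2 and m = 50 the measured values differ 25-fold. The geometric mean then differs 5-fold at f = 50% (5.000/1.000) but only 1.38-fold at f = 90% (0.792/0.574). The median equals LLOQ/2 once f exceeds 50%.

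**The case against.** The strongest reply is that nothing in the trial turns on this. The rule is explicit and prespecified. No hypothesis test uses Day 1 or Week 64 concentrations, and no between-arm comparison of baseline concentration is planned. ADA categories rest on assay response and titer (SAP 2.1.5), and associations between ADA and concentration only may be explored (SAP 2.4.6.1.2). A careful reader would also spot the artefact, since minimum, median and maximum would all equal one constant at Day 1. All of this stands, and it limits the severity. It does not make the predose value right.

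The wording about drug-treated patients might be read as patients already dosed, which would exempt the predose sample. The paired sentence about patients in the placebo group points to treatment group instead. If the narrower sense is meant, the SAP should say so.

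A reader might go further and infer that Week 64 values are expected to be undetectable and that the rule therefore sets the Week 64 means. The documents do not support that. The only basis is another trial, with weekly dosing for 16 weeks, at the end of a 16-week follow-up, and no assay limit or proportion of patients is given. Here Arm A is 14 weeks off drug. SAP 2.1.4 still counts the period to 98 days after the last dose as residual treatment. The Week 64 window in SAP Table 5 opens after Day 406, which is 55 days after a Week 50 dose on Day 351. The inference is plausible, more so for Arm B than for Arm A, but it is not established.

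**Conclusion.** The concern holds for Day 1 and for placebo. As written, the rule produces a predose concentration of LLOQ/2 with CV 0% in Arms A and B against 0 in placebo, and a placebo geometric mean that carries no information. This assumes only that predose values are below the limit and that the rule applies by treatment group.

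For Week 64 the conclusion is conditional. The constant may dominate the geometric mean and median if a large share of values is below the limit. The arithmetic mean is mainly substitution only when that share reaches roughly 80% to 99%, for quantifiable values at 2 to 50 times LLOQ. The documents give neither the share nor the LLOQ, so the size cannot be fixed.

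Severity is minor. The effect stays within descriptive pharmacokinetic summaries, on-treatment troughs change little if few are below the limit, and Week 64 data collected after the Week 52-based lock go to a report addendum (SAP section 4).

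**What to change.** In SAP 2.4.6.1.1:
- Set Day 1 predose values below LLOQ to 0 in every arm, and show the Day 1 geometric mean as not calculated.
- Do not compute geometric means for the placebo group.
- Report n (%) below LLOQ by visit and arm, so that summaries driven by substitution can be recognised. State the LLOQ with the tables.

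Limiting visits with a high share below LLOQ to median and range is optional; the threshold for doing so is a matter of convention.

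The cost is a few lines of SAP text and programming. No extra data are needed and no efficacy analysis changes.

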2.4.6.1.2 Analyses of ADA variables

The following summary will be provided based on ADA population:

- Number (%) of patients with pre-existing immunoreactivity
- Number (%) of patients with treatment-emergent ADA
- The summary statistics (including number, median, Q1, Q3, minimum and maximum) of the peak post-baseline titer for patients with treatment-emergent ADA, and patients with persistent, indeterminate and transient ADA response
- Number (%) of patient with transient treatment-emergent ADA
- Number (%) of patients with persistent treatment-emergent ADA
- Number (%) of patients with indeterminate treatment-emergent ADA
- Number (%) of patients with treatment-boosted ADA
- The summary statistics (including number, median, Q1, Q3, minimum and maximum) of the peak post-baseline titer for patients with treatment-boosted ADA
- The summary statistics (including number, mean, SD, median, Q1, Q3, minimum and maximum) of the ratio of peak post-baseline titer to baseline titer for patients with treatment-boosted ADA
- Listing of ADA peak titer levels and neutralizing antibody status
- Number(%) of patients with neutralizing antibody status

Kinetics of treatment-emergent ADA response

Number (%) of patients with treatment-emergent ADA positive response at each visit will be summarized by each treatment group.

Plot of percentage of patients with treatment-emergent ADA positive response at each visit will be provided by each treatment group.

Impact of ADA on PK

Associations between ADA variables (eg, ADA peak titers, neutralizing antibody status, treatment-emergent, persistent, indeterminate and transient response, treatment-boosted) and serum concentration of dupilumab may be explored for each dupilumab dose group. Plot of serum concentration of functional SAR231893 (REGN668) versus visit will be provided by ADA classifications for each dupilumab dose group. Individual patient plots of PK according to ADA status will be provided to determine which individuals may have had PK impacted by ADAs.

Association of ADA with clinical efficacy endpoints

Associations between the ADA variables (eg, ADA peak titers, neutralizing antibody status, treatment-emergent, persistent, indeterminate and transient response, treatment-boosted) and the co-primary efficacy endpoints may be explored for the dupilumab dosed group.

Association of ADA with clinical safety endpoints

Association of safety versus ADA status may be analyzed in the ADA population. The safety assessment may focus on the following events:

Severe injection site reactions last longer than 24 hours or serious injection site reactions

- Hypersensitivity reactions (SMQ (20000214) hypersensitivity narrow search confirmed by medical review)
- Anaphylactic reactions (SMQ (20000021) anaphylactic reaction narrow search)
- In response to AESI like anaphylaxis or hypersensitivity additional ADA samples closer to the event may be analyzed, based on the judgment of the medical investigator and/or medical monitor.
- Associations between ADA variables (eg, ADA peak titers, neutralizing antibody status, treatment-emergent and treatment-boosted) and safety may be explored.

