2.4.4.1 Analysis of primary efficacy endpoint(s)

Co-primary efficacy variables

The co-primary efficacy variables are: change from baseline in NC and in NPS (change from baseline in NC, NPS and LMK for Japan) at Week 24 assessed for dupilumab 300 mg q2w (pooled A and B arms) versus placebo, respectively.

The following null hypothesis and alternative will be tested for pooled dupilumab arms against placebo:

- H0: No treatment difference between the dupilumab dose regimen and placebo.
- H1: There is a treatment difference between the dupilumab dose regimen and placebo

Primary statistical model (ITT analysis)

Each of the 2 co-primary efficacy endpoints (3 co-primary efficacy endpoints for Japan) will be analyzed using a hybrid method of the worst-observation carried forward (WOCF) and multiple imputation. Data collected after treatment discontinuation will be included in the analysis. With this approach, for patients who undergo surgery for NP or receive SCS for any reason, data collected postsurgery (actual date) or post SCS will be set to missing, and the worst postbaseline value on or before the time of surgery or SCS will be used to impute missing Week 24 value (for patients whose postbaseline values are all missing, the baseline will be used to impute). For patients who discontinue the treatment without being rescued by surgery or receiving SCS, a multiple imputation approach will be used to impute missing Week 24 value, and this multiple imputation will use all patients who have not been rescued by surgery or receiving SCS at Week 24. Each of the imputed complete data will be analyzed by fitting an ANCOVA model with the baseline value of the corresponding co-primary endpoint, treatment group, asthma/NERD status, prior surgery history, and regions as covariates. Statistical inference obtained from all imputed data will be combined using Rubin's rule. Descriptive statistics including number of patients, mean, standard error, and least squares (LS) means will be provided. In addition, difference in LS means and the corresponding 95% confidence intervals (CI) will be provided along with the p-values.

Imputation and analysis model will be built with the following sample SAS code:

1. 40 datasets with a monotone missing pattern will be obtained, induced by Markov Chain Monte Carlo (MCMC) method on patients who have not been rescued by surgery or receiving SCS at Week 24.

```
proc mi data=dat_etd seed=14280 nimpute=40 out=dat_mc;  

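### The exploratory ADA–efficacy association would set ADA status from samples taken up to Week 52 or 64 against outcomes fixed at Week 24

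*SAP*

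**What the plan says.** SAP 2.4.6.1.2 (Analyses of ADA variables) allows associations between ADA variables "and the co-primary efficacy endpoints may be explored for the dupilumab dosed group". Its examples are peak titer, neutralizing status, treatment-emergent response, the persistent, indeterminate and transient classes, and boosted response. No model is given.

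The outcome is fixed in time. SAP 2.4.4.1 defines the co-primary variables as changes from baseline "at Week 24 assessed for dupilumab 300 mg q2w (pooled A and B arms) versus placebo, respectively".

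The ADA variables are not limited in time:
- Treatment-emergent (SAP 2.1.5): "A positive response in the ADA assay post first dose, when baseline results are negative or missing".
- Boosted (SAP 2.1.5): "An ADA positive response in the assay post first dose that is greater-than or equal to 4-fold over baseline titer levels", where baseline is positive.
- Indeterminate (SAP 2.1.5): "defined as a treatment-emergent response with only the last collected sample positive in the ADA assay".
- Titer (SAP 2.4.6.1.2): the "peak post-baseline titer for patients with treatment-emergent ADA".
- Sampling (SAP 2.1.5): status at Day 1 and "Week 8, Week 16, Week 24, Week 52 and follow up at Week 64 will be provided".

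Neither document restricts ADA to samples taken before the Week 24 outcome for this association, uses time of onset, or adds a sensitivity analysis on the point.

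**The concern.** The purpose of relating ADA to efficacy is to see whether antibodies weaken the response. That needs the antibody status to precede, or at least coincide with, the response. Under the stated definitions, a patient negative at Weeks 8, 16 and 24 and first positive at Week 52 belongs to the ADA-positive group when Week 24 nasal congestion and polyp scores are compared.

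Such patients mix an unexposed subgroup into the exposed group. If their Week 24 results resemble those of never-positive patients, a real loss of efficacy would look smaller than it is, and the analysis would lean towards reassurance.

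**Working it through.** **Inputs.** Post-dose ADA samples at Weeks 8, 16, 24, 52 and 64 (SAP 2.1.5), target Days 57, 113, 169, 365 and 449 (SAP Tables 3 to 5). Outcome at Week 24, Day 169. Assumed NC benefit 0.55 with SD 1.03, assumed NPS benefit 1.24, 240 patients in the dupilumab pool (SAP 1.3).

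**The plan's own figure.** The documents state no figure for the ADA analysis. As background, the NC power was checked: with 25% dropout (180 versus 90), difference 0.55, SD 1.03 and two-sided 0.05, power is 98.5% against the stated 99%.

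**Time order.**
- Week 52: 365 − 169 = 196 days = 28 weeks after the outcome.
- Week 64: 449 − 169 = 280 days = 40 weeks after it.
- Two of the five post-dose samples fall after the outcome.

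**The response classes.**
- Indeterminate: in a patient sampled to Week 52 or 64, only the last sample is positive, so Weeks 8, 16 and 24 were not. For these patients the class is entirely post-outcome. This needs no assumption about incidence.
- Persistent: consecutive positives must span more than 84 days. Weeks 16 to 24 span 56 days and Weeks 8 to 24 span 112. By Week 24, at the scheduled visits, only an unbroken run from Week 8 qualifies.
- Transient: Weeks 52 and 64 are nominally 449 − 365 = 84 days apart, which is not more than 84. A patient positive only at those two visits would fall here on nominal dates, again wholly after the outcome.

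**Dilution, if late positives match never-positives at Week 24.** Let D be the true Week 24 difference for patients positive by Week 24, and f the share of ever-positive patients who were positive by then. The ever-positive versus never-positive contrast is f × D + (1 − f) × 0 = f × D, so the dilution is 1 − f. The value of f must be assumed:

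| Assumption | f | Dilution | NC 0.55 appears as | NPS 1.24 appears as |
|---|---|---|---|---|
| To Week 52, equal new positives per sample | 3/4 = 0.75 | 25% | 0.41 | 0.93 |
| To Week 52, constant rate over time | 24/52 = 0.46 | 54% | 0.25 | 0.57 |
| To Week 64, equal new positives per sample | 3/5 = 0.60 | 40% | 0.33 | 0.74 |
| To Week 64, constant rate over time | 24/64 = 0.375 | 62.5% | 0.21 | 0.47 |

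The last two columns suppose, for illustration only, that ADA removes the whole assumed benefit. A simulation at f = 0.375 and 0.60 gave NC contrasts of 0.21 and 0.32, in line with the formula.

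**Does a smaller positive group cost power?** Assume 10% incidence (24 of 240), f = 0.60, an NC loss of 0.55 and no dropout.
- All-sample status: SE = 1.03 × √(1/24 + 1/216) = 0.222; 0.33/0.222 = 1.49; power about 32%.
- Status by Week 24: 0.60 × 24 = 14.4 positives; SE = 1.03 × √(1/14.4 + 1/225.6) = 0.280; 0.55/0.280 = 1.96; power about 50%.

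Under these assumptions the smaller, correctly timed group is the more informative one.

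**The case against.** The strongest reply is that little rests on this analysis. It is optional in the SAP, and Protocol 11.4.4.2 is equally permissive about ADA impact on efficacy. It lies outside the hierarchy in SAP 2.4.4.3, and the list of variables is given by example. An analyst could choose Week 24 status without breaching the plan. The SAP also commits to treatment-emergent positivity by visit and treatment group, so a reader would see how much of it appears late. All of this stands and limits the weight of the point. It does not remove it: the only definitions available are unlimited in time, and the by-visit summary is not linked to efficacy.

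Several stronger readings are tempting, and the documents do not support them:
- *That any ADA effect is necessarily diluted.* This depends on late positives resembling never-positives. If low exposure drove both a weak Week 24 response and later ADA, late positives would exaggerate the association.
- *That the 40–62% range describes the study report.* SAP Section 4 locks the database when all patients have completed Week 52 or discontinued, so Week 64 samples will be incomplete at that point. Week 52 positives alone create the problem.
- *That patients who leave early drift into the ADA-negative group.* Protocol 10.3.1 keeps scheduled ADA sampling after treatment is stopped, to Week 52 or Week 64 depending on timing. Only study withdrawals and missed samples lose ADA data.
- *That ADA arising under Arm B's q4w phase counts against q2w efficacy.* Late positives with ordinary Week 24 results would make the ADA-positive group look better, not worse.

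**Conclusion.** The point holds as a time-order fault in an exploratory analysis. Following SAP 2.1.5 as written, patients first positive 28 or 40 weeks after the Week 24 outcome would be counted as ADA-positive for it. For those sampled to Week 52 or 64, the indeterminate class consists of nobody else.

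The likely effect is dilution, on the condition that late positives resemble never-positives at Week 24. Its size cannot be derived from the documents. Under the two onset patterns assumed above, it is about 25–54% with samples to Week 52 and about 40–62% with samples to Week 64. No confirmatory test, error rate or success criterion is affected. The change is worth making because it is cheap.

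**What to change.** In SAP 2.4.6.1.2, state that for associations with the Week 24 co-primary endpoints, treatment-emergent and boosted status, peak titer and neutralizing status are derived only from samples dated on or before the patient's Week 24 efficacy assessment. Use actual sample dates. A cut by visit label would not work, because the ADA window labelled Week 24 in SAP Table 5 runs over Days 141–266, up to 97 days past Day 169.

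Do not use the persistent, indeterminate and transient classes as main explanatory variables at Week 24, since they depend on later samples. If they are shown, label them as whole-study classes. For any association with Week 52 endpoints, use ADA up to the Week 52 assessment, by arm. Keep the whole-study classification for the incidence tables.

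The cost is a short SAP addition and one extra derived flag from samples already planned, with fewer ADA-positive patients in the Week 24 association. There is a precedent: SAP 2.4.5.1 and 2.4.5.3 to 2.4.5.5 already add summaries restricted to Week 24 for adverse events, laboratory values, vital signs and ECG.
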